## 9.7 Data analysis

A detailed description of statistical methods will be documented in a separate statistical analysis plan (SAP) to be finalised before data collection is completed.

Analyses will be performed by pH Associates using Stata (StataCorp LLC) and Microsoft Excel. Data from all participating centres will be pooled for analysis.

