#### Milestones

Start of data collection: Jun 2018. End of data collection: Dec 2018.

Final report of study results: Feb 2019.

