## 6. Milestones

Milestone	Planned date
Registration in the EU PAS register	Apr 2018
Start of data collection	May 2018
Interim analysis (for submission to ASH 2018)	July 2018
End of data collection	Dec 2018
Publication at ASH 2018	Dec 2018
Publication at EHA 2019	Jun 2019
Final report of study results	Feb 2019

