#### 9.7.1 Primary analyses

For the primary endpoint analyses, the frequency and proportion of patients receiving CT-P10 who experience IRRs on day 1 or day 2 after the index event will be presented with 95% CI. The proportional Z-test will be used to compare the IRR rate observed in this study with rates previously reported for reference rituximab in the literature.

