#### 9.7.4 Subgroup and sensitivity analyses

Subgroup analyses may be conducted to further evaluate the safety and clinical effectiveness of CT-P10 in patients with NHL or CLL. This may include, but will not be limited to:

- Diagnosis (NHL [further stratified by FL / DLBCL] / CLL).
- Infusion time for the index event (90 minutes, 60<90 minutes, <60 minutes).
- Patients with / without prior exposure to a rituximab-containing regimen.

No sensitivity analyses are planned.

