#### 9.7.5 Interim analyses

Interim analyses are planned in order to submit data to the American Society of Hematology (ASH) 2018 and European Hematology Association (EHA) 2019 Annual Meetings.

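### The SAP deadline is tied to the end of data collection (December 2018), not to the July 2018 interim analysis, so the Z-test comparator and the subgroup list may be fixed after partial data have been analysed

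*Protocol*

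**What the plan says.** **SAP deadline.** Section 9.7 leaves the detailed methods to a separate SAP, "to be finalised before data collection is completed". No other deadline for it is given.

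**Calendar.** The abstract has "End of data collection: Dec 2018", and section 6 agrees. The section 6 table also has a row "Interim analysis (for submission to ASH 2018", dated July 2018. Section 9.7.5 confirms the purpose: "Interim analyses are planned in order to submit data to the American Society of Hematology (ASH) 2018", with a second congress in 2019. It gives no endpoints, data cut or number of patients. The abstract has "Start of data collection: Jun 2018", whereas section 6 says May 2018.

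**Comparator.** Under section 9.7.1 the primary endpoint is reported as a frequency and proportion with a 95% CI. The section then adds a test: "The proportional Z-test will be used to compare the IRR rate observed in this study" with "rates previously reported for reference rituximab in the literature". No source, value, significance level or sidedness is stated.

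**Subgroups.** Section 9.7.4 makes subgroup analyses optional, names three, and introduces them with "This may include, but will not be limited to".

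**The concern.** A protocol may leave the comparator and the exact subgroups to the SAP. That protects the analysis only if the SAP is settled before anyone sees results. Here the deadline is linked to the end of data collection, although an earlier analysis is already on the calendar. The study is single-arm and retrospective, so no concealed allocation hides the IRR rate from those who write the SAP.

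At stake is the credibility of the Z-test comparison and of any subgroup result. If the reference rate is picked once an interim IRR rate is known, a statement that the observed rate is above, or not different from, published experience may reflect that choice. The final report could not show otherwise from the protocol alone.

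**Working it through.** **1. Dates side by side**

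| Event | Date | Source |
|---|---|---|
| Data collection starts | May or June 2018 | Section 6; abstract |
| Interim analysis for the first congress | July 2018 | Section 6 |
| Latest date for a final SAP | Before data collection ends, December 2018 | Section 9.7 with section 6 |

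July to December is five months. The interim falls one to two months after collection starts, so its data would be partial. The IRR endpoint covers day 1 or day 2 after the index infusion and needs no six-month follow-up, so it is likely to be among the first results available. That is an inference.

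**2. What is fixed and what is open**

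- Fixed: index event, rapid infusion, IRR, survival, progression and response definitions (section 2.2); primary endpoint and its window, and the six-month AE window (section 9.3); censoring rules (section 9.7.2); the list of IRR terms (Annex 3).
- Open: the rate or rates for the Z-test (section 9.7.1), the subgroup list (section 9.7.4) and the interim content (section 9.7.5).

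**3. The protocol's own precision figure**

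Section 9.5 gives 6.8% to 14.0% for a 10% rate with 300 patients. The exact (Clopper-Pearson) interval for 30/300 is 6.8% to 14.0%, so the figure is reproduced. It contains no reference rate, so the choice of comparator cannot change it.

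**4. How far the Z-test depends on the reference rate**

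Inputs: n = 300 (section 9.5). The reference rates are the pooled 8.84% and its upper 95% limit, 10.81%, both in section 9.5. Section 9.5 uses the pooled figure for study size only. The upper limit serves here as a stand-in for another literature value one might choose. Two-sided 0.05 is assumed, in line with the 95% CI.

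Formula: z = (p − p0) / √(p0(1 − p0)/n).

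For an illustrative 39/300 = 0.130:

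- p0 = 0.0884: standard error √(0.0884 × 0.9116/300) = 0.01639; z = 0.0416/0.01639 = 2.54; p = 0.011.
- p0 = 0.1081: standard error √(0.1081 × 0.8919/300) = 0.01793; z = 0.0219/0.01793 = 1.22; p = 0.22.

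Non-significant counts out of 300, from p0 ± 1.96 standard errors:

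- p0 = 8.84%: 17 to 36 events (5.7% to 12.0%).
- p0 = 10.81%: 22 to 42 events (7.3% to 14.0%).

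The two reference rates therefore give different verdicts at 17 to 21 events (5.7% to 7.0%) and at 37 to 42 events (12.3% to 14.0%). At 22 to 36 events, which includes the 10% planning rate (30/300), both give a non-significant result.

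**The case against.** The strongest reply is that little is left to steer. The study is declared descriptive, without a hypothesis. Its primary objective is to describe incidence, and its size rests on precision. The proportion and its interval do not depend on any reference rate. The protocol already cites 8.84% in a dated document, so a later switch would be visible. The plural wording about literature rates may mean comparison with several of them. The named subgroups carry no confirmatory claim. Comparator values and subgroup lists are ordinary SAP content, and the SAP is not at hand.

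Most of this stands, and it limits the point. It does not answer the timing rule, which the protocol itself states. Section 9.7.1 still places a test within the primary analysis, and nothing requires its comparator to be settled before July 2018. Comparing with several rates does not help unless they are named in advance.

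A reader might infer more than the text supports:

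- **That the definitions are open too.** They are not (step 2 of the working). Changing them would take an amendment under section 9.10.
- **That the primary data are analysed in July.** The protocol says only that there is an interim analysis. No endpoints are stated, and the final IRR rate would not be known then.
- **That one result could support three opposite conclusions**, because 39/300 is also far below the roughly 30% of the highest study (z = −6.43). Section 9.5 uses that figure only to illustrate interval width and does not propose it as a comparator.
- **That the SAP was late.** The wording allows this but does not show that it happened.

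**Conclusion.** The concern holds in a limited form. The stated rule permits the Z-test comparator and the subgroup list to be fixed up to five months after partial data have been analysed for a congress. The exposure ends there: the descriptive IRR proportion and its 95% CI are unaffected, and with no declared hypothesis no formal type I error claim is lost.

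The size is modest. Within the range of the cited meta-analysis, moving the reference from the pooled rate to its upper limit changes the test verdict only for observed rates of 5.7% to 7.0% or 12.3% to 14.0%. This rests on the full 300 patients (an interim would have fewer), a two-sided 0.05 level, and 39/300 as a hypothetical result. That the interim includes the IRR endpoint is probable but not stated. The change is cheap and worth making, but it does not bear on the study's validity as a descriptive estimate.

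**What to change.** Amend section 9.7 so that the SAP is finalised and dated before the first interim data cut (July 2018). The SAP should name:

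- the comparator rate or rates for the Z-test, with their source;
- the subgroup list;
- the content of each interim analysis: endpoints, data cut and patients included.

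Anything added afterwards should be labelled post hoc in the report. The IRR definition and the AE windows need no change on this account.

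Cost: no extra patients or data, and no sample-size figure changes. The downside is that SAP work planned for any time up to December must be done before July.

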#### 9.7.1 Primary analyses

For the primary endpoint analyses, the frequency and proportion of patients receiving CT-P10 who experience IRRs on day 1 or day 2 after the index event will be presented with 95% CI. The proportional Z-test will be used to compare the IRR rate observed in this study with rates previously reported for reference rituximab in the literature.

#### 9.7.2 Secondary analyses

For the secondary endpoint safety analyses, rates of events per-patient-per month will be reported. Secondary clinical effectiveness endpoints will be reported separately for patients with NHL or CLL. The time-to-event clinical effectiveness endpoint analyses (OS, PFS, time to complete or partial response) and CT-P10 treatment duration will be displayed descriptively using Kaplan Meier plots from the index event until the date of the event or censoring. Patients who are known to be alive at 6 months post-index will be censored on that date for OS whereas patients who are lost to follow-up will be censored at the date they were last known to be alive (i.e. the last recorded hospital visit within the 6 months post-index). For PFS, patients will be censored on the date they were last known not to have disease progression (i.e. the date of last documented response assessment) and for time to complete or partial response, patients will be censored at the date of the last recorded known response. For treatment duration, censoring will occur at the 6 months post-index date (if CT-P10 treatment is known to be ongoing at 6 months) or the date of the last infusion (if the patient is lost to follow-up). Absolute counts and the percentages of these events occuring in each disease indication group will be reported. Survival rates for 6 months post NHL or CLL diagnosis will also be calculated. Summary data will be tabulated and also displayed graphically where appropriate.

The proportion of patients assessed as having a best response of complete response, partial response, stable disease or progressive disease within the 6 months post-index based the documented assessment of the local investigator and the proportion of patients with a complete or partial response, will be presented with 95% CI.

For the demographic, clinical, and NHL/CLL disease characteristics endpoint analyses, the study population will be described by means of summary statistics. Distributions and descriptive statistics of both central tendency (medians and means) and dispersion (standard deviation, interquartile range [IQR]) will be presented for

quantitative variables. Categorical variables will be described with frequencies and percentages; distributions, modes, medians, IQR and range will be reported as appropriate. 95% CI will be presented for means and estimates of proportions, as appropriate. Where appropriate differences between disease groups will be evaluated using two-sample t-tests or Mann-Whitney U-tests for continuous normally and non-normally distributed variables, respectively, while the chi-squared test will be employed for nominal variables. Normality of variables will be evaluated through inspecting histograms of their distributions.

Treatment patterns for NHL or CLL in patients who receive rapid infusion of CT-P10 will be described for the entire study period. Summary statistics will be displayed for the treatment dose and duration on treatment, and for the treatment discontinuation reason.

All percentages will be reported to the nearest whole number; therefore, in reporting study results in tables, figures and associated text, percentages may not add up to 100% due to rounding.

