#### • **Serious adverse event (SAE):** a SAE is an AE that:

- is fatal
- o is life threatening (places the subject at immediate risk of death)
- o requires in-patient hospitalisation or prolongation of existing hospitalisation
- results in persistent or significant disability/incapacity
- o is a congenital anomaly/birth defect
- other significant medical hazard.

- **Adverse event grade:** AEs will be defined as grade 1, 2, 3, 4 or 5 according to the Common Terminology Criteria for Adverse Events v4.0 (CTCAE).
- **Overall survival (OS):** defined as the time from the index date to death from any cause.
- **Progression free survival (PFS):** defined as the time from the index date to the first documented evidence of disease progression or death from any cause. The assessment of disease progression will be based on the International Workshop on Chronic Lymphocytic Leukemia (IWCLL) criteria for CLL or the Revised Response Criteria for Malignant Lymphoma for NHL, if these criteria are used and documented locally. If different criteria are used in routine practice, disease progression will be defined as documented in the medical records.
- Complete response (CR) or partial response (PR): will be based on IWCLL criteria for CLL or the Revised Response Criteria for Malignant Lymphoma for NHL, if these criteria are used and documented locally. If different criteria are used in routine practice, response will be defined as documented in the medical records.

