#### 9.2.3 Observation period

Data will be collected retrospectively for each patient from the date of diagnosis of NHL or CLL until the index date and for a period of 6 months post-index (or until death, if sooner).

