# Endpoint to address the secondary objective

# Variables required to address the secondary objective

Secondary objective 1: To describe the safety profile of rapidly infused CT-P10 in patients with NHL or CLL in the 6 months post-index date

- Proportion of patients who experience the following safety events in the 6 months post-index date, and frequency of each per patient per month:
  - Any IRR.
  - Any grade 3 or grade 4 IRR (according to the Common Terminology Criteria for Adverse Events [CTCAE] version 4).
  - Any other AE (excluding IRR).
  - Any other grade 3 or grade 4 AE (excluding IRR).
  - o Any serious adverse event (SAE).
- Proportion of patients with AEs as the primary cause for treatment discontinuation.
- Summary distributions of event type by grade.
- Proportion of all rapid CT-P10 infusions during which IRRs were experienced.

For all AEs (temporally associated with CT-P10 treatment) during the 6 months post-index (including the index date):

- Description of AE
- IRR (Yes/No)
- Event start date
- Event end date
- Seriousness
- CTCAE v4.0 grade
- Clinician's assessment of relationship to CT-P10
- AE resulted in treatment discontinuation (Yes/No).

Secondary objective 2: To describe the clinical effectiveness of rapidly infused CT-P10 in patients with NHL or CLL in the 6 months post-index

- OS, defined as the time from the index date until death from any cause.
- Proportion of patients surviving at six months following NHL or CLL diagnosis and following the index date.
- PFS, defined as the time from the index date until the first documented evidence of disease progression or death from any cause.
- Proportion of patients surviving and free from disease progression at six months following the index date.
- Summary of best response to CT-P10

- Date of data collection.
- Patient alive at 6 months post-index (Yes / No / Not known)?
- If no, date of death (DD/MM/YYYY).
- All treatment response assessments in the post-index period (date, recorded treatment response [complete response / partial response / no response or stable disease / progressive disease], assessment based on IWCLL / Revised Response Criteria for Malignant Lymphoma / local criteria / other criteria, type(s) of

- (complete response / partial response / no response or stable disease / progressive disease).
- Proportion of patients achieving a complete or partial response.

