- Time to complete or partial response, defined as the number of days from the index date until first documentation of complete or partial response by the local investigator.
- assessments used to evaluate response).
- Date (within 6 months post-index) of last recorded hospital visit.

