#### 9.7.3 Missing data

Where data are missing from the original medical record, the affected analyses will be conducted using only the results of those patients with data available and the number included in each analysis will be stated.

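### PFS is censored at the last response assessment while deaths and documented progressions count up to 6 months, which can bias the Kaplan-Meier curve downward when assessments are irregular

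*Protocol*

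**What the plan says.** Section 9.3 defines PFS as "the time from the index date until the first documented evidence of disease progression or death from any cause". Section 2.2 names published criteria for progression and adds a fallback: "If different criteria are used in routine practice, disease progression will be defined as documented in the medical records". Follow-up under section 9.2.3 runs "for a period of 6 months post-index (or until death, if sooner".

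For patients without an event, section 9.7.2 states that "patients will be censored on the date they were last known not to have disease progression (i.e. the date of last documented response assessment". In the same paragraph, overall survival is handled differently: patients known to be alive at 6 months are censored at 6 months, and those lost to follow-up at their last hospital visit. The data for that rule are collected under section 9.3, namely vital status at 6 months and "Date (within 6 months post-index) of last recorded hospital visit".

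On response, section 9.7.2 says that "for time to complete or partial response, patients will be censored at the date of the last recorded known response". Section 9.7.3 says that where data are missing, "the affected analyses will be conducted using only the results of those patients with data available", with the number included to be stated.

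Section 9.9 expects assessments to be irregular and less frequent than in a trial. The only PFS bias it names is upward, from late detection of progression. Section 9.7.4 plans no sensitivity analysis.

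**The concern.** Take two patients whose last assessment was at month 3. One dies at month 5 and stays in the risk set until month 5. The other is alive at month 6 with no progression on record and leaves the risk set at month 3. Their time at risk differs only because their outcomes differ. Late in the window the risk set then over-represents patients who are about to have an event, and each event removes too large a share of the curve.

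Censoring at the last disease assessment is a conventional PFS rule where scans follow a fixed calendar and there is a rule for events after missed scans. This retrospective study has neither, and its window closes at a fixed 6 months. A reader guided by section 9.9 would expect the published curves to err upward when they may err downward, possibly by much more.

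Response has a related, smaller problem. The time-to-response rule gives no usable date for a patient who was never assessed and does not say how death before response is treated. If unassessed patients leave the denominator, the response rate rises.

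**Working it through.** **Plan's own figure.** There is none: the protocol states no PFS rate, event count or PFS-based precision. The event rates and assessment patterns below are assumptions.

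**Inputs.** NHL group of 240 (section 9.5). Assumed 6-month death 5% and progression 10%, so true PFS = 0.95 × 0.90 = 0.855. That gives 240 × 0.855 = 205.2 event-free patients and 34.8 with an event. Everyone is assessed at month 3, and a fraction f again at month 6.

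**Case A: progressions are recorded on their own date.** With events spread evenly, 17.4 fall before month 3 and 17.4 after.
- S(3) = 1 − 17.4/240 = 0.9275.
- After month 3 the risk set is the 17.4 patients with an event to come plus 205.2f event-free patients.
- S(6) = 0.9275 × 205.2f / (205.2f + 17.4).
- For f = 0.5: 0.9275 × 102.6/120.0 = 0.793.

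**Case B: progressions surface only at an assessment**, so only deaths can follow the last one.
- Per half-window, √0.95 = 0.9747 survive and √0.90 = 0.9487 do not progress, so S(3) = 0.9247.
- S(6) = 0.9247 × [0.9747f / (0.9747f + 0.0253)] × 0.9487.
- For f = 0.5: 0.9247 × 0.9506 × 0.9487 = 0.834.

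**Alternative: patients without a recorded event are censored at 6 months.** Case A returns 0.855 exactly. Case B gives 0.9247 × 0.9747 × (1 − 0.0513f), because progressions not yet found count as event-free.

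| f assessed at month 6 | Planned rule, case A | Planned rule, case B | 6-month censoring, case B |
|---|---|---|---|
| 1.0 | 85.5% | 85.5% | 85.5% |
| 0.7 | 82.7% | 84.6% | 86.9% |
| 0.5 | 79.3% | 83.4% | 87.8% |
| 0.3 | 72.3% | 80.7% | 88.7% |
| 0 | 0% | 0% | 90.1% |

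The last row is the extreme: after month 3 only patients who go on to have an event remain at risk, so the curve falls to zero. Simulating the rows from 0.3 to 0.7 gives about 72 to 84% across both cases.

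**Sparser or earlier last assessments.** These need simulation. At the same event rates, with many patients having no or one assessment, or with last assessments spread over months 4 to 6, the planned curve averages about 39 to 68% at 6 months. Other choices of assessment dates within these patterns lower the bottom end to about 33%. Spread over months 4 to 6, the average is about 67% in case A and 62% in case B.

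**Second setting, true PFS 90%, 30% of events deaths, case A, n = 240.**
- Months 3 and 6 for all: 90.0%.
- Month 3 for all, month 6 for 70%: 88.1%.
- Last assessment spread over months 4 to 6: 75.7%.
- Last assessment spread over months 2 to 6: 63.1%.

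For a CLL group of 60, the last pattern averages 69.3%. With months 4 to 6 the average is 78.0%, but individual simulated studies land anywhere from 0% to about 97%, because one late event with few patients left at risk can collapse the curve.

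**Response.** If 25% are unassessed and 80% of the assessed respond (both assumed), the assessed-only rate is 80%, while responders among all patients are 0.75 × 0.80 = 60%.

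**The case against.** **The rule is conventional, and patients are not known to be event-free after their last assessment.** This stands. A reader might infer that the plan discards time in which patients are known to be progression-free. The documents do not support that: after the last assessment they are known to be alive at most, with no progression on record.

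**Assessments are not limited to scans.** Section 9.3 collects every post-index response assessment under any criteria, and progressive disease is a category of that same variable. A late visit recorded as stable disease therefore extends follow-up, and mainly deaths fall after the last assessment. This stands in part. It makes case B the more relevant one where many are assessed at month 6, and there the bias is about 1 to 5 points. It does not rescue patterns in which assessments end earlier: case B still gives about 62% for months 4 to 6.

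**The 6-month proportion may not come from the curve.** A reader might infer that the listed endpoint, alive and progression-free at six months, will be badly wrong. Section 9.3 lists it separately from PFS, and section 9.7.2 also promises counts and percentages. Nothing says it is read from the Kaplan-Meier curve, and crude percentages do not carry this bias in the same way. This stands, although the plan should say how the proportion is derived.

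**Section 9.7.3 does not expressly remove early deaths from the response denominator.** This is correct. It covers data missing from the record and promises the number analysed. The 80% against 60% contrast shows only what could happen under assumed inputs.

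**The alternative has its own bias.** This stands: undetected progression counts as event-free. In the table this adds 1.4 to 4.6 points wherever f is below 1. Section 9.9 already discloses that direction of error.

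**Conclusion.** The censoring rule in section 9.7.2 depends on outcome and can bias the Kaplan-Meier PFS curve downward. The bias is nil if nearly everyone is assessed at month 6, about 1 to 13 points if 30 to 70% are, and tens of points if last assessments fall well before month 6. These sizes rest on assumed death and progression rates and assumed assessment dates. The stronger statement, that 6-month PFS will certainly come out far too low, is not supported, because the protocol does not show when patients are assessed. What is established is that the rule leaves the result exposed to assessment timing and that section 9.9 names only the opposite direction.

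The response points are smaller and concern rules left open. PFS and response are secondary, descriptive endpoints without a hypothesis, and the primary infusion-reaction result is untouched. This should be fixed.

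**What to change.** 1. In section 9.7.2, add a Kaplan-Meier PFS analysis that censors patients known alive with no documented progression at 6 months, and all other event-free patients at the last recorded hospital visit. Show it beside the last-assessment curve. In the scenarios examined the two err in opposite directions or not at all, so together they roughly bracket the result. Amend section 9.7.4 accordingly.
2. State that the proportion alive and progression-free at six months is not read from the last-assessment curve.
3. Add the possible downward bias to section 9.9.
4. Report the response rate over all patients in the disease group, counting death or progression before assessment as non-response, beside the assessed-only rate. Show time to response as cumulative incidence with death as a competing event.

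The cost is a few sentences and one extra curve per disease. Vital status and last-visit date are already collected, so no new data are needed. The drawback is that undetected progression counts as event-free in the added curve, which should be said next to it.

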## 2.2 Key definitions

- **Index event:** first rapid infusion of CT-P10 (note: first rapid infusion must have been given as part of the second or a subsequent treatment cycle).
- **Index date:** date of first rapid infusion of CT-P10 (note: first rapid infusion must have been given as part of the second or a subsequent treatment cycle) (day 1).
- **Rapid infusion:** defined as a total infusion time for CT-P10 of 90 minutes or less.
- **Infusion-related reaction (IRR):** any adverse event (AE) from a pre-defined list (see Annex 3) occurring on day 1 or day 2 after an infusion of CT-P10.
- Pre-index observation period: the pre-index observation period for this study
  will be from the date of diagnosis of NHL or CLL until the index date, and will be
  used to capture patients' demographic and clinical characteristics.
- Post-index observation period: patients will be observed for a period of 6
  months after the index date (or until death, if sooner), to capture safety and
  clinical outcomes.
- Adverse event (AE): An AE is any untoward medical occurrence in a patient administered a pharmaceutical product and which does not necessarily have to have a causal relationship with this treatment. An AE can therefore be any unfavourable and unintended sign (including an abnormal laboratory finding, for example), symptom, or disease temporally associated with the use of a medicinal product, whether or not considered related to the medicinal product. The definition of an AE includes worsening of a pre-existing medical condition.

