## 9.2 Setting

#### 9.2.1 Study population

The source population for this study is adult patients with NHL or CLL who received treatment with rapidly infused CT-P10 as part of their standard clinical care in five European countries.

Patients fulfilling the following criteria will be potentially eligible for inclusion in the study:

- Patients with a confirmed diagnosis of NHL (follicular lymphoma [FL] or diffuse large B-cell lymphoma [DLBCL]) or CLL.
- Patients who had received rapidly infused CT-P10 for their second or a subsequent treatment cycle; 'rapidly' defined as 90-minutes or less.
- Patients at least 18 years of age at the date of diagnosis of NHL or CLL.
- Patients (or next of kin, if appropriate locally) providing written informed consent for study data collection (if this is required according to local country regulations).

Patients fulfilling any of the following criteria will be excluded from the study:

- Patients who had received reference rituximab for any previous treatment cycles
   (i.e. prior to the index event) within the same line of treatment.
- Patients whose medical records are unavailable for review.

As only limited exclusion criteria will be applied, and patients will be included from a range of centres in five European countries, it is expected that the study population will be representative of the overall source population.

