# Secondary objective 4: To describe the baseline demographic, clinical and disease characteristics of patients with NHL or CLL who receive treatment with rapidly infused CT-P10.

Demographic and clinical characteristics (at index date unless specified)

- Summary measures of patients' age, sex, ethnicity, employment status, comorbidities (Charlson Comorbidity Index ), disease duration and prior chemotherapy and rituximab exposure.
- Number of other diagnosed malignancies.
- Summary of Eastern Cooperative Oncology Group (ECOG) performance status at closest time point prior to the index date.
- Summary measures of duration of CT-P10 infusion(s) given prior to the index event.
- Proportion of patients who experienced IRRs with CT-P10 infusion(s) given prior to the index event (by IRR grade).

- Month and year of birth
- Index date
- Date of diagnosis of NHL or CLL
- Sex (male/female)
- Ethnicity
- Employment status (full time / part time / unemployed / student / retired / home-maker) at closest time point prior to index date and date documented.
- Relevant comorbidities ongoing at index date (components of Charlson Comorbidity Index will be captured)
- Prior treatment regimens for NHL or CLL from diagnosis of NHL or CLL to the index date (name and type of treatment, start date, stop date [for

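### Six-month survival counted from diagnosis is biased upward, because every patient must be alive at a later rapid infusion to enter the study

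*Protocol*

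**What the plan says.** Protocol section 9.7.2 plans the analysis: "Survival rates for 6 months post NHL or CLL diagnosis will also be calculated". In section 9.3, under secondary objective 2 (clinical effectiveness), the matching endpoint is "Proportion of patients surviving at six months following NHL or CLL diagnosis and following the index date". One bullet therefore holds two rates with different time origins.

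Entry is set in section 9.2.1: "Patients who had received rapidly infused CT-P10 for their second or a subsequent treatment cycle". Section 2.2 defines the index event as the first rapid infusion and adds that the "first rapid infusion must have been given as part of the second or a subsequent treatment cycle". The pre-index period in the same section "will be from the date of diagnosis of NHL or CLL until the index date", with no upper limit on its length.

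The secondary objective itself (section 8.4) is confined to effectiveness in the 6 months after the index date. OS and PFS are defined from the index date in section 2.2.

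**The concern.** A patient who died after diagnosis but before a qualifying rapid infusion cannot be in the dataset. The time from diagnosis to index is therefore immortal: it adds survival time to the rate but can never add a death. For a patient whose index falls 6 months or more after diagnosis, the whole window is immortal and six-month survival is certain.

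Long gaps are allowed. Section 9.3 (secondary objective 4) collects "Prior treatment regimens for NHL or CLL from diagnosis of NHL or CLL to the index date", and section 9.7.4 foresees a subgroup of "Patients with / without prior exposure to a rituximab-containing regimen". The reported rate thus depends partly on how long before index the patients were diagnosed. NHL and CLL are reported separately, so if their typical gaps differ, the two figures are biased by different amounts.

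The rate also covers time before rapid infusion began, so it does not answer the post-index objective under which it is listed. The limitations in section 9.9 warn of upward bias in PFS for another reason (infrequent assessment) and do not mention this one.

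**Working it through.** The protocol gives no figure for this rate, so there is nothing to reproduce. The direction of the bias follows from the eligibility rule; the size can only be illustrated.

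**Direction.** Let T be survival time from diagnosis and L the gap from diagnosis to index, in months. The rate is meant to describe P(T > 6). Because inclusion requires T > L, a patient with gap L contributes P(T > 6 | T > L):

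- for L of 6 or more, this equals 1;
- for L between 0 and 6, with constant hazard and six-month survival S, it equals S^((6 − L)/6), which exceeds S whenever S is below 1.

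**By gap (assumed S, constant hazard).**

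| True six-month survival | L = 1 | L = 2 | L = 3 | L = 4 | L ≥ 6 |
|---|---|---|---|---|---|
| 80% | 83.0% | 86.2% | 89.4% | 92.8% | 100% |
| 90% | 91.6% | 93.2% | 94.9% | 96.5% | 100% |
| 95% | 95.8% | 96.6% | 97.5% | 98.3% | 100% |

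**For a mixed sample.** Assumptions, none from the protocol: monthly mortality m; a share p of included patients indexed at 6 months or later; the rest indexed at 1.5 months, leaving 4.5 months at risk.

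- True rate = (1 − m)^6
- Planned rate = p + (1 − p)(1 − m)^4.5

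Worked case, m = 2% and p = 50%: true = 0.98^6 = 88.6%; planned = 0.5 + 0.5 × 0.98^4.5 = 95.7%; excess 7.1 points.

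| Monthly mortality | True | Planned, p = 25% | Excess (points) | Planned, p = 75% | Excess (points) |
|---|---|---|---|---|---|
| 0.25% | 98.5% | 99.2% | 0.7 | 99.7% | 1.2 |
| 0.5% | 97.0% | 98.3% | 1.3 | 99.4% | 2.4 |
| 1% | 94.1% | 96.7% | 2.5 | 98.9% | 4.7 |
| 3% | 83.3% | 90.4% | 7.1 | 96.8% | 13.5 |

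Excesses are computed before rounding.

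**What delayed entry recovers.** A simulation of 2,000,000 patients before selection used gaps of 1, 2, 3, 4 and 12 months, equally likely, and a constant hazard:

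| True six-month survival | Simple proportion among those included | Kaplan-Meier with delayed entry, months 1 to 6 | True survival from month 1 to 6 |
|---|---|---|---|
| 80% | 89.6% | 83.0% | 83.0% |
| 90% | 95.1% | 91.6% | 91.6% |

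Delayed entry removes the bias from the first index time onward. It does not give back the 80% or 90%, because nobody is under observation before month 1.

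**The case against.** The strongest reply is that little depends on this number. The primary endpoint is the proportion with an infusion-related reaction on day 1 or 2. OS and PFS, with their Kaplan-Meier plots, start at index, and the same bullet in section 9.3 also gives six-month survival from index. The study is descriptive, and the from-diagnosis rate enters no planned test or decision. All of this stands, and it limits the severity.

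Second, as the proportion of these study patients alive six months after their diagnosis, the figure is arithmetically correct, and section 9.9 already cautions about generalisability. That is fair as far as it goes. However, the rate is listed as a measure of clinical effectiveness, is not labelled as conditional on reaching a rapid infusion, and the caution in 9.9 does not describe this mechanism.

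Third, section 9.7 leaves detailed methods to the SAP, which might specify delayed entry. A reader might infer that the protocol rules this out; it does not, since it names no estimator for this rate. The point rests on what the protocol does fix: a diagnosis origin, and a simple proportion with no conditioning.

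Two further readings are tempting and unsupported. One is that the study's effectiveness evidence as a whole is inflated by this; the index-based endpoints do not share the problem. The other is that the rate will be published as a general survival rate for NHL and CLL; the protocol does not say so.

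**Conclusion.** The point holds and should be fixed, though it is not critical. As a measure of survival after diagnosis, the planned rate is biased upward for any gap above zero if patients can die in that interval, and it is 100% by construction for patients indexed at 6 months or later. It also falls outside the post-index objective. One descriptive secondary output is affected.

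The size is not known. The illustrative overstatement runs from about 0.7 points (0.25% monthly mortality, 25% indexed late) to about 13.5 points (3%, 75% late). It rests wholly on assumed constant mortality and an assumed timing mix, since the protocol states neither. A reader might take 95.7% against 88.6% as an estimate for this study; it is only one chosen scenario.

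**What to change.** Delete the from-diagnosis survival rate from sections 9.3 and 9.7.2, and keep six-month survival from the index date. This is the cleaner repair.

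If a from-diagnosis figure is kept:

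- estimate it by Kaplan-Meier with delayed entry at the index date;
- label it as survival conditional on reaching the earliest index time;
- show the numbers at risk;
- state the limitation in section 9.9.

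The cost is small. Diagnosis, index and death dates are already collected, so no new data are needed. The downside is that one descriptive output is lost, or becomes less favourable and less precise. Early risk sets may be small, particularly in CLL, where section 9.5 expects about 60 patients.
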